## 5      Restrictions for Study Subjects

During recruitment, screening/informed consent review, and baseline visit, the subjects must be informed and reminded of the following restrictions:

### 5.1    Contraception requirements

Please refer to exclusion criteria ([Section 4.2](#)) for details of contraception requirements for the study.

### 5.2    Prohibited treatment

Use of the treatments displayed in the table below are NOT allowed during the screening period or after the start of study treatment due the concern for increased potential immunosuppressant-related conditions. These are prohibited for the duration of the study until 30 days after the last study visit.

**Table 5-1      Prohibited treatment**

Medication	Action to be taken
Biologic drugs targeting the systemic immune system (e.g., TNF- $\alpha$ blockers, anakinra, rituximab, abatacept, tocilizumab)	Discontinue study drug
Live vaccines (within 90 days of study drug dosing)	Discontinue study treatment; if live vaccines are given after screening but prior to study drug administration, the subject may be enrolled after 90 days have passed since vaccine administration if the subject continues to meet eligibility criteria upon re-screening
Systemic immune suppressive drugs, except for the following: prednisone $\leq$ 15 mg/d and/or no more than one of the following cytotoxic drugs: methotrexate, azathioprine, leflunomide or hydroxychloroquine, provided dosing of these listed medications has remained unchanged in a 12 week period prior to randomization and remains unchanged throughout study period	Any acute dosing of immune suppressive drugs may require discontinuation of study treatment and participation and will have to be evaluated with Sponsor on a case-by case basis

### 5.3    Dietary restrictions and smoking

There are no specific dietary restrictions except for those required when preparing for PET scanning. Subjects are not allowed to participate in the trial if they smoke.

### 5.4    Other restrictions

On study days when spirometry will be performed, patients should refrain from the following:

- Using of bronchodilators for at least 6 hours for short-acting  $\beta$ -2 agonist and at least 48 hours for long-acting  $\beta$ -2 agonist prior to spirometry testing
- Drinking alcohol for 4 hours prior to spirometry testing
- Participating in strenuous activity for 30 min prior to spirometry testing
- Wearing clothes that substantially restrict full chest and abdominal expansion
- Eating a large meal within 2 hours of testing

On study days when [F-18]FDG-PET/CT scan is performed, patients should:

- Refrain from alcohol consumption and vigorous sports activities 24 hours prior to the measurement
- Be well-hydrated and fasted 4 hours prior to administration of radiotracer
- Have a blood glucose level below 11 mmol/L (200 mg/dL)

## **6 Treatment**

### **6.1 Study treatment**

Details on the storage and management of study medication, randomization and instructions for prescribing and taking study treatment are outlined in Section 3 of the Site Operations Manual.

#### **6.1.1 Investigational treatment and control drugs**

The investigational drug, ACZ885 (canakinumab) 150 mg/ 1mL and matching placebo liquid in vials will be prepared by Novartis and supplied to the Investigator as blinded subject packs.

#### **6.1.2 Additional study treatment**

- [F-18]fluorodeoxyglucose ([F-18]FDG) PET tracer will be produced under GMP. [F-18]FDG PET has approved New Drug Application in the US and marketing authorities in the EU for certain indications. [F-18]FDG will be sourced locally.
- Salbutamol/Albuterol will be used during the spirometry testing and will be sourced locally.

### **6.2 Treatment arms**

Subjects will be assigned to one of the following two treatment arms in a ratio of 1:1. Study treatments are defined as:

- Doses of 300 mg ACZ885 s.c. every four weeks
- Doses of placebo to match the 300 mg ACZ885 s.c. every four weeks

### **6.3 Treatment assignment and randomization**

All eligible subjects will be randomized via Interactive Response Technology (IRT) to one of the treatment arms. The investigator or his/her delegate will contact the IRT after confirming that the subject fulfills all the inclusion/exclusion criteria. Subjects will undergo stratification based on baseline [F-18] FDG-PET/CT results. The IRT will assign a randomization number to the subject, which will be used to link the subject to a treatment arm and will specify a unique medication number for the first package of investigational treatment to be dispensed to the subject. The randomization number will not be communicated to the caller.

The randomization numbers will be generated using the following procedure to ensure that treatment assignment is unbiased and concealed from subjects and investigator staff. A subject randomization list will be produced by the IRT provider using a validated system that automates the random assignment of treatment arms to randomization numbers. Once a

patient is deemed eligible for enrollment into the study and ready for dosing, the next lowest available randomization number will be assigned. These randomization numbers are linked to the different treatment arms, which in turn are linked to medication numbers. A separate medication list will be produced by or under the responsibility of Novartis Drug Supply Management using a validated system that automates the random assignment of medication numbers to packs containing the investigational drug.

#### **6.4 Treatment blinding**

This is a subject- and investigator-blinded study; subjects, investigator staff, and persons performing the assessments will remain blind to the identity of study treatments according to the specifications provided in [Table 6-1](#).

The identity of the treatments will be concealed by the use of study drugs that are all identical in packaging, labeling, schedule of administration, appearance, taste and odor.

Randomization data are kept strictly confidential, and are accessible only to authorized personnel, until unblinding of the trial as described in the blinding table ([Table 6-1](#)). The clinical team may communicate unblinded interim analysis results (e.g., information needed for planning/modifying another study) to relevant Novartis teams for information, consulting and/or decision purposes.

No further dissemination of interim results should occur, in particular not with individuals involved in treating the study's subjects or assessing clinical data (e.g., ECGs, images, symptoms) obtained in the study.

Unblinding will occur in the case of patient emergencies (see [Section 6.7](#)), at the time of interim analysis and at the conclusion of the study.

#### **Site staff**

Unblinding a single subject at site for safety reasons (necessary for subject management) will occur via an emergency system in place at the site (see [Section 6.7](#)).

#### **Sponsor staff**

The following unblinded sponsor roles are required for this study:

Unblinded sample analyst(s) (PK/PD/IG)

The sample analysts will receive a copy of the randomization schedule (via request to the Randomization Office), to facilitate analysis of the samples. The sample analysts will provide the sample data to the study team under blinded conditions unless otherwise allowed.

The study statistician will be able to access the randomization list for interim analyses and is allowed to share unblinded information with the rest of the clinical team as appropriate for internal decision purposes, as outlined in [Table 6-1](#). For example, unblinded summaries and unblinded individual data can be shared with the team for interim analyses.

Study programmers and other personnel involved in study data analysis (e.g., biomarker expert) are allowed to access treatment assignment information for the purpose of conducting interim analyses.

**Table 6-1** **Blinding levels**

Role	Time or Event			
	Randomization list generated	Treatment allocation & dosing	Safety event (single subject unblinded)	Interim Analysis & dose escalation
Subjects/Patients	B	B	UI	B
Site staff	B	B	UI	B
Unblinded site staff (see text for details)	NA	NA	NA	NA
Drug Supply and Randomization Office	UI	UI	UI	UI
Unblinded sponsor staff (see text for details)	UI	UI	UI	UI
Statistician/statistical programmer/data analysts	B	B	UI	UI
Independent committees used for assessing interim results	NA	NA	NA	NA
All other sponsor staff not identified above	B	B	UI	UI

B Remains blinded

NA Not applicable

UI Allowed to be unblinded on individual patient level

## 6.5 Treating the subject

ACZ885 will be administered to the subject via the following route of administration (s.c. injection) at the investigational site. See the Site Operations Manual for further details.

Sponsor qualified medical personnel will be readily available to advise on trial-related medical questions or problems.

## 6.6 Permitted dose adjustments and interruptions of study treatment

Scheduled dosing of study drug may be delayed by up to 5 days if subjects present with conditions that require withholding of study drug, e.g., evidence for active infection (treated or untreated) or acute abdominal pain. Outside of this 5-day window, the dose will be considered missed. These changes must be recorded on the Dosage Administration Record CRF. The 5-day window for those subjects requiring study drug to be withheld until resolution is in addition to the defined +/-5 day visit window, therefore subjects can be no more than 10 days outside of the scheduled visit. Subjects must maintain at least 21 days between visits.

Subjects who are unable to generate the requisite number of reproducible spirometry maneuvers at baseline will be allowed an additional 5 days beyond the 40-day screening period, if necessary, for repeat spirometry prior to dosing. All other baseline measures should be repeated at the same visit as the first dose administration.

Subjects are able to miss no more than one dose administration. All missed dose administrations must be discussed with the Sponsor to determine if the subject should be discontinued from further study treatment.

## **6.7 Emergency breaking of assigned treatment code**

Emergency treatment code breaks must only be undertaken when it is required to in order to treat the subject safely. Most often, study treatment discontinuation and knowledge of the possible treatment assignments are sufficient to treat a study subject who presents with an emergency condition. Emergency treatment code breaks are performed using the IRT. When the investigator contacts the system to break a treatment code for a subject, he/she must provide the requested subject identifying information and confirm the necessity to break the treatment code for the subject. The investigator will then receive details of the investigational drug treatment for the specified subject and a fax or email confirming this information. The system will automatically inform the study monitor for the site and the study team that the code has been broken.

It is the investigator's responsibility to ensure that there is a dependable procedure in place to allow access to the IRT in case of emergency. The investigator will need to provide:

- protocol number
- study drug name (if available)
- subject number

The investigator must provide oral and written information to inform the subject how to contact his/her backup in cases of emergency when he/she is unavailable to ensure that unblinding can be performed at any time and instructions for contacting the local Novartis CPO (or any entity to which it has delegated responsibility for emergency code breaks) to the subject in case an emergency treatment code break is required at a time when the investigator and backup are unavailable.

## **6.8 Treatment exposure and compliance**

Pharmacokinetic parameters (measures of treatment exposure) will be determined in all subjects treated with ACZ885, as detailed in [Section 8.7](#).

## **6.9 Recommended treatment of adverse events**

There is no treatment that can reverse the activity of ACZ885. Given that ACZ885 is an IgG1 isotype monoclonal antibody, plasmapheresis may be of value in removing ACZ885 from the body. Potential adverse events should therefore be treated symptomatically at the discretion of the Investigator. Medication used to treat AEs must be recorded on the concomitant medications/significant non-drug therapies eCRF.

## **6.10 Rescue medication**

In the context of this study, rescue medications are defined as those medications used acutely to directly manage medical signs or symptoms related to the subject's underlying sarcoidosis. Addition or alteration of immunosuppressant or corticosteroid therapy for or by a patient during the study are not allowed and may require his or her termination from study participation. If a patient is withdrawn from the study, the Week 32 EOS visit should be completed.

### **Non-sarcoidosis flares (bronchitis)**

Patients with sarcoidosis may experience episodes of bronchitis that do not indicate worsening of their disease. Production of yellow-green sputum is a characteristic of bronchitis. Treatment details are at the discretion of the investigating physician. First line treatment is typically with antibiotics. Unresponsive patients may require the addition of a short course of corticosteroids. This may result in the patient being withdrawn from the trial (See [Table 5-1](#)) in which case the Week 32 EOS visit should be completed.

### **Acute pulmonary exacerbations of sarcoidosis (APES)**

APES are defined as acute worsening of pulmonary signs and symptoms in patients with known sarcoidosis not explained by another cause, combined with a decline in spirometry ( $\geq 10\%$  decrease from previous baseline FVC and/or FEV1, present for at least one month ([Panselinas and Judson 2012](#))). Patients' signs and symptoms of APES typically respond to corticosteroids. This may result in the patient being withdrawn from the trial (See [Table 5-1](#)) in which case the Week 32 EOS visit should be completed.

Use of rescue medication must be recorded on the concomitant medications/significant nondrug therapies CRF.

### **6.11 Concomitant treatment**

The investigator must instruct the subject to notify the study site about any new medications he/she takes after the subject was enrolled into the study.

Common potential concomitant medications in this study population are anticipated to include topical corticosteroids or systemic corticosteroids at  $\leq 15$  mg/d prednisone or equivalent, and/or up to one of the following systemic immune-modulating drugs: methotrexate, azathioprine, leflunomide or hydroxychloroquine.

All prescription medications, over-the-counter drugs and significant non-drug therapies (including physical therapy and blood transfusions) administered or taken within the timeframe defined in the entry criteria prior to the start of the study and during the study must be recorded on the concomitant medications/significant non-drug therapies CRF.

Medication entries should be specific to trade name, the single dose and unit, the frequency and route of administration, the start and discontinuation date and the reason for therapy.

## 7 Study completion and discontinuation

### 7.1 Study completion and post-study treatment

Each subject will be required to complete the study in its entirety and thereafter no further study treatment will be made available to them. Study completion is defined as when the last subject completes their EOS visit, and any repeat assessments associated with this visit have been documented and followed-up appropriately by the Investigator, or in the event of an early study termination decision, the date of that decision.

A follow-up visit or phone call for SAEs must be performed 30 days following early discontinuation, or 8 weeks after last injection of study drug, whichever is later. The phone call for SAEs is kept as source documentation. All SAEs reported during this time period must be reported as described in [Section 9.2](#) and the Site Operations Manual. Documentation of attempts to contact the subject should be recorded in the source documentation.

### 7.2 Discontinuation of study treatment

#### Individual subject withdrawal

Subjects may voluntarily discontinue from the study for any reason at any time. They may be considered withdrawn if they state an intention to withdraw, fail to return for visits, or become lost to follow-up for any other reason.

Any patient who discontinues the study early will complete the Week 32 EOS visit. For those patients discontinuing after Week 12, the volumetric and HRCT exam should also be included as assessed on a case-by-case basis by the Sponsor.

If a subject discontinuation occurs for any reason, the Investigator must make every effort to determine the primary reason for a subject's discontinuation from the study and record this information on the CRF.

The investigator should discontinue study treatment for a given subject or discontinue the subject from study if, on balance, he/she believes that continuation would be detrimental to the subject's well-being.

If a liver or renal event occurs, follow guidelines outlined in [Appendix 1](#) and [Appendix 2](#) regarding discontinuation of study treatment.

Study treatment must be permanently discontinued under the following circumstances:

- Subject withdraws consent
- Pregnancy
- Severe allergic reaction or anaphylaxis following administration of the study drug
- Non-compliance as defined by missing more than one dose administration
- Emergence of the following adverse events:
  - Serious infections combined with neutropenia CTCAE v4.03 grades  $\geq 1$  (ANC  $< 1.5 \times 10^9/L$ )
  - Confirmed diagnosis of latent or active TB
  - Onset of any malignancy

- Any of the following laboratory abnormalities confirmed to be sustained by repeat assessment within 7 days after initial lab assessment:
  - Neutropenia CTCAE v4.03 grades  $\geq 2$
  - Thrombocytopenia CTCAE v4.03 grade 4
- Use of prohibited treatment as per [Table 5-1](#).
- Any other protocol deviation that results in a significant risk to the patient's safety

The appropriate personnel from the site and Novartis will assess whether study treatment should be discontinued for any subject whose treatment code has been broken inadvertently for any reason.

Subjects who discontinue study treatment should NOT automatically be considered withdrawn from the study. See [Section 8](#) for the required assessments of these subjects after discontinuation of study treatment.

### **7.3 Withdrawal of informed consent**

Subjects may voluntarily withdraw consent to participate in the study for any reason at any time.

Withdrawal of consent occurs only when a subject does not want to participate in the study anymore **and** does not want any further visits or assessments **and** does not want any further study-related contact **and** does not allow analysis of already obtained biologic material.

If a subject withdraws consent, the investigator must make every effort to determine the primary reason for this decision and record this information. Study treatment must be discontinued and no further assessments conducted. All biological material that has not been analyzed at the time of withdrawal must not be used. Further attempts to contact the subject are not allowed unless safety findings require communicating or follow-up.

### **7.4 Lost to follow-up**

For subjects whose status is unclear because they fail to appear for study visits without stating an intention to withdraw, the investigator should show "due diligence" by documenting in the source documents steps taken to contact the subject, e.g., dates of telephone calls, registered letters, etc. A subject should not be considered lost to follow-up until his/her scheduled end of study visit would have occurred.

### **7.5 Study Stopping rules**

All subjects will undergo regular monitoring at scheduled visits for safety and tolerability, including adverse events, throughout the duration of the study. If significant risk to the study subjects is identified, the study may be put on hold or terminated based on a full safety review.

The study will be stopped if any of the following criteria are met, and no further dosing pending a full safety review:

- An overt change in the rate of incidence of expected drug-related serious adverse events such as infections, opportunistic infections, hypersensitivity, white blood cell (WBC) or platelet count decreases as compared to the rates described in the current version of the IB.

- New unexpected serious adverse events considered related to canakinumab in more than 3 individuals on active therapy.

## **7.6 Early study termination by the sponsor**

The investigator must contact the IRT to register the subject's discontinuation from the study and/or investigational treatment. The study can be terminated by Novartis at any time for medical or ethical reasons, and/or in accordance with the respective contractual terms. Should this be necessary, the subject should be seen as soon as possible and treated as a prematurely withdrawn subject as described in [Section 7](#). The investigator may be informed of additional procedures to be followed in order to ensure that adequate consideration is given to the protection of the subject's interests. The investigator will be responsible for informing institutional review boards (IRBs) and/or ethic committees (ECs) of the early termination of the trial.

## 8 Procedures and assessments

### 8.1 Assessment Schedule

	Epoch	Screening	Treatment							End of Study 	
	Study Phase	Screening	Treatment Period 								
		Visit Numbers 	1	101	102	103	104	105	106		
	Study Day(s)		40 to 0 -40 +0	1	29 -5 +5	57 -5 +5	85 -5 +5	113 -5 +5	141 -5 +5	169 -5 +5	224 -5 +5
Informed consent		S									
Inclusion / exclusion criteria		S	S								
Medical history/current medical conditions		X									
Demography		X									
Physical examination		S	S	S	S	S	S	S	S	S	
Smoking history		X									
Tuberculosis Blood Test		S									
Hepatitis and HIV Screen		S									
Urine drug screen and cotinine test		S									
Pregnancy test 		X	X							X	
Hematology		X	X	X	X	X	X	X	X	X	
Blood chemistry		X	X	X	X	X	X	X	X	X	
Urinalysis 		X	X	X	X	X	X	X	X	X	
Body height		X									
Body weight		X				X					
Body temperature		X	X	X	X	X	X	X	X	X	
Blood pressure 		X	X	X	X	X	X	X	X	X	
Spirometry		X		X	X	X	X	X		X	
Spirometry Reversibility Test			X 						X		
Diffusing Capacity (DLCO)				X	X	X	X	X	X	X	

 Visit structure given for internal programming purpose only

 A window of  $\pm 5$  days is allowed for the treatment visits, but the interval between 2 doses must be at least 21 days

 All patients who discontinue early must complete the EOS Visit. For those discontinuing after week 12, the volumetric and HRCT exam should also be included as assessed on a case-by-case basis by the Sponsor

 Limited to females of childbearing age. Serum testing is done at screening and urine test is done predose at Day 1 and at the EOS

 If the dipstick result is positive for protein, nitrite, leukocytes and/or blood, the sample should be sent for microscopic analysis of WBC, red blood cell count (RBC) and casts

 Vital signs taken after resting in a sitting position for at least 3 minutes

 For subjects at baseline who are unable to generate reproducible spirometry maneuvers, an additional 5 days beyond the 40 day screening window will be allowed for the subjects to return for repeat spirometry.

 Oxygen saturation %, pulse rate, and Borg Questionnaire score will be recorded before the test. Oxygen saturation %, pulse rate, Borg Questionnaire score, and distance walked will be recorded at the end of the test. 6MWT should occur after ECGs have been completed. Pulse rate should be taken after sitting for at least 3 minutes.

 The screening HRCT should be completed as the last assessment for eligibility criteria. If patients have evidence of parenchymal involvement of disease from historical radiological evidence (e.g. CT, MRI or x-ray), then baseline HRCT can be performed at same time as the [F-18]FDG-PET/CT. At each time point, two scans will be collected: 1 HRCT scan and 1 lower dose volumetric CT scan.

 The [F-18]FDG-PET/CT requires a blood glucose level below 11 mmol/L. The measurement is performed by finger prick at site the same day [F-18]FDG-PET/CT is performed

 For baseline, [F-18]FDG-PET/CT results obtained within 8 weeks of randomization will be accepted. The [F-18]FDG-PET/CT at baseline should always be conducted after all other assessments are done and patient found eligible unless a previous result was used or sponsor agreement was obtained. It should not be done post-randomization.

 All assessments for a given visit should be completed before study drug is administered

Corporate Confidential Information

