### 2.2 Secondary objectives

Secondary objectives	Endpoints related to secondary objectives

To determine the effect of ACZ885 on decreasing the maximum standardized uptake value (SUVmax) [F-18]FDG-PET in nodules (nodular uptake regions) after 12 weeks of treatment, compared to placebo.

	

Percent change from initial scan in [F-18]FDG-PET SUVmax at week 12

To determine the effect of ACZ885 versus placebo on other parameters of pulmonary function testing (i.e., absolute FVC, FEV1, FEV1/FVC, FEV3, FEF25-75, FEV3/FVC, FEV6, TLC, RV, RV/TLC, DLco and post-bronchodilator FEV1/reversibility) in patients with sarcoidosis at 24 weeks compared to baseline

	

Lung function testing results at 24 weeks compared to baseline

To determine the effect of ACZ885 versus placebo on HRCT of patients with sarcoidosis at 24 weeks compared to initial HRCT scan as measured by side-by-side comparison by blinded reviewers and HRCT scoring

	

HRCT results at 24 weeks compared to HRCT initial scan measured by blinded reviewers and HRCT scoring

To determine the effect of ACZ885 versus placebo on the 6-minute walk test (6MWT) distance of patients with sarcoidosis at 12 and 24 weeks compared to baseline

	

6MWT results at week 12 and 24 compared to baseline

Secondary objectives	Endpoints related to secondary objectives

• To determine the effect of ACZ885 on additional [F-18]FDG-PET outcomes (i.e., SUVmean, SUVpeak and volume of the lesions) after 12 weeks of treatment compared to placebo

	

• Percent change from initial scan in additional [F-18]FDG PET outcomes at week 12

• To assess the safety and tolerability of ACZ885 in patients with sarcoidosis as measured by adverse events (AEs)

	

• Adverse events in patients taking ACZ885 compared to placebo

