### Rationale for other secondary outcomes

Full pulmonary function tests include spirometry (FVC, FEV1, FEV1/FVC, FEF25-75, FEV3/FVC, FEV6, lung volumes (TLC, RV, RV/TLC) and gas diffusion (DLco) to allow further characterization of the patients' response to treatment. Emerging evidence suggests that sarcoidosis involves a component of small airways disease caused by constriction by peribronchiolar granulomatous inflammation (Davies et al 2000). Therefore, the following spirometry measures: FEV3, FEV3/FVC, 1-(FEV3/FVC) will be performed to assess small airway disease. (Burgel et al 2011). The Investigator needs to pay special attention to capture the FEV3 data (not always captured by traditional software; may be captured by saving the flow volume loop).

The 6MWT (including distance walked, changes in oxygenation, and Borg Questionnaire) is a practical and simple assessment of functional capacity, reflective of activities of daily living (Enright 2003) that has been increasingly applied to assess various lung diseases, including interstitial lung diseases other than sarcoidosis where it has proved useful for both predicting mortality and monitoring response to therapy. Its application in sarcoidosis studies has been more limited (Baughman et al 2007) and results should be interpreted in recognition of the multi-factorial nature of the disease (Baughman and Lower 2011).

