### **8.5.5.4 Spirometry Reversibility Test**

Two spirometry evaluations will be performed at Visit 101 and Visit 107, the first prior to use of salbutamol/albuterol, the second performed after intake of salbutamol/albuterol. The initial spirometry assessment will be performed after a wash-out period of at least 6 hours for a short-acting  $\beta$ -2 agonist and at least 48 hours for a long acting  $\beta$ -2 agonist. After the initial spirometry assessment salbutamol/albuterol is administered, and the second spirometry assessment is performed within 30 min of administration. Investigators should follow the reversibility procedures cited in the ATS/ERS guidelines above with regard to bronchodilator use. The primary spirometry readout will be the post-bronchodilator FVC.

Reversibility (%) will be calculated as follows:

(FEV1 (post bronchodilator) – FEV1 (pre-bronchodilator) x 100)/FEV1 (pre-bronchodilator)

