### **6.1.1 Variables**

The primary variable will be the change from baseline in percent predicted FVC after 24 weeks of treatment. The FVC is measured at screening, day 1, week 4, week 8, week 12, week 16, week 20 and week 24. Baseline is defined as day 1. At the visits (day 1 and week 24) where pre- and post-bronchodilation assessments are done, the pre-bronchodilation values are used.

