## **6.2 Secondary objectives**

### **6.2.1 Variables**

Secondary variables for this study are:

- [F-18]FDG-PET/CT
- HRCT
- Pulmonary function tests: Change from baseline in absolute and % predicted FVC, FEV1, FEF25-75, FEV1/FVC, FEV3, FEV3/FVC, FEV6, TLC, RV, RV/TLC, DLCO, and post-bronchodilator FEV1/reversibility and other parameters as needed
- 6MWT outcomes: Change from baseline in distance, oxygen saturation, hearth rate and Borg Questionnaire score

For the pulmonary function test parameters the direction of benefit is as follows

- an increase in values is beneficial: absolute and % predicted FVC, FEV1, FEF25-75, FEV1/FVC, FEV3, FEV6, FEV3/FVC, DLCO
- a decrease in values is beneficial: RV, TCL, RV/TCL.

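### The DLco row of the Protocol 8.1 schedule marks no visit before the first dose, although DLco change from baseline is a planned secondary endpoint

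*Protocol*

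**What the plan says.** **The endpoint.** Protocol 2.2 names DLco among the other pulmonary function parameters. The endpoint is "Lung function testing results at 24 weeks compared to baseline". SAP 6.2.1 lists change from baseline for a set of parameters that ends with "RV/TLC, DLCO, and post-bronchodilator FEV1/reversibility and other parameters as needed". The only baseline definition for lung function is in SAP 6.1.1, written for FVC: "Baseline is defined as day 1".

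**The schedule.** In Protocol 8.1 the row "Diffusing Capacity (DLCO" carries seven marks, on Days 29, 57, 85, 113, 141, 169 and 224, and none at Screening or Day 1. Footnote 12 adds that "All assessments for a given visit should be completed before study drug is administered", so any Day 1 test would be pre-dose.

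**The text.** The rationale for other secondary outcomes in Protocol 2.2 describes full pulmonary function tests as spirometry plus "lung volumes (TLC, RV, RV/TLC) and gas diffusion (DLco) to allow further characterization of the patients' response to treatment". Protocol 3.1 calls for a full clinical baseline before the injection and counts pulmonary function tests among the baseline assessments. Protocol 4 also speaks of pulmonary function tests at first baseline. Where Protocol 3.1 names DLco itself, it leaves the timing to the Assessment Schedule. Protocol 8.5 does the same for all efficacy assessments, and Protocol 8.5.5.1 gives a method for DLco but no visits.

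**The concern.** A change from baseline needs a value taken before treatment, and the schedule is where sites look for visit timing. As the row stands, the first DLco would come four weeks after the first injection. A missed pre-dose value cannot be recovered later. A site is also not free to fill the gap on its own initiative, because Protocol 13 forbids investigators to add procedures for research purposes.

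The baseline statements in Protocol 3.1 and 4 do not settle the matter. They refer to pulmonary function tests in general, and Day 1 spirometry alone would satisfy them. If they are instead read together with the description of full tests in Protocol 2.2, the text requires a baseline DLco that the schedule does not show. On either reading one part of the plan needs correcting.

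**Working it through.** The plan gives no figure to reproduce here. The check is a reading of the table, followed by a comparison with the text.

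**1. Fix the columns.** The header of the machine-read table is damaged: the visit numbers stop at 106, and the header fields do not line up with the body rows. The hematology row has nine marks, which matches the nine visits: Screening and Days 1, 29, 57, 85, 113, 141, 169 and 224. I used it to set the column positions.

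**2. Test the columns on rows whose visits are also stated elsewhere.**

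| Row | Visits read from the table | Independent statement | Agrees |
|---|---|---|---|
| Pregnancy test | Screening, 1, 224 | Footnote 4: "Serum testing is done at screening and urine test is done predose at Day 1 and at the EOS" | Yes |
| Spirometry reversibility | 1, 169 | Protocol 8.5.5.4: "Two spirometry evaluations will be performed at Visit 101 and Visit 107" | Yes |
| Spirometry and reversibility together | Screening, 1, 29, 57, 85, 113, 141, 169, 224 | SAP 6.1.1: FVC at screening, Day 1 and Weeks 4, 8, 12, 16, 20 and 24 | Yes; the schedule adds Day 224 |

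For the last row, week = (day − 1)/7: (29 − 1)/7 = 4, and so on to (169 − 1)/7 = 24.

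**3. Read the DLco row.** Its marks fall on Days 29, 57, 85, 113, 141, 169 and 224. Of the two possible pre-dose visits, Screening and Day 1, 0 of 2 are marked. The row has as many cells as the hematology row, so no cell has simply dropped out.

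**4. Look for another explanation.** The checks in step 2 make a shift of the whole table unlikely. They do not exclude a shift of this row alone: seven marks would also fit Days 1, 29, 57, 85, 113, 141 and 169, the seven treatment visits. DLco is also the last row before the copy breaks off. Footnotes 8 to 12 belong to rows that are not shown, so the lung-volume row cannot be used as a comparison.

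**5. What is lost if the row is right.** Change from baseline cannot be computed at a site that follows it. The Week 24 comparison between arms remains valid under randomisation but loses baseline adjustment. If r is the correlation between baseline and Week 24 DLco, the variance of the unadjusted comparison relative to a baseline-adjusted one (ANCOVA) is 1/(1 − r²). The documents give no r, so these values are assumptions:

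- r = 0.5: 1/(1 − 0.25) = 1.3
- r = 0.8: 1/(1 − 0.64) = 2.8
- r = 0.9: 1/(1 − 0.81) = 5.3

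With about 15 patients per arm expected to provide Week 24 data (Protocol 11.7), that is a real loss for anyone who wants to estimate a DLco effect.

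**6. What is not affected.** FVC has a Day 1 value through the reversibility row, so the primary endpoint stands. Protocol 11.5.1.3 only lists, summarises and graphs the other lung function data. The lung function model in SAP 6.2.3 covers FEV1, FEV3 and FEV6, not DLco.

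**The case against.** The strongest reply is that the evidence is one row of a broken table, while the text already provides for baseline pulmonary function tests and elsewhere describes such tests as including DLco. A separate pulmonary function manual, not available here, may give the visits. The row may be an extraction fault, and sites may in practice test DLco on Day 1.

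Much of this stands. It is why the PDF must be checked first, and why it is not established that patients will lack a baseline. It does not remove the point, because the text hands DLco timing to the schedule and never places DLco on Day 1.

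A reader might infer two stronger things:

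- **That the DLco objective cannot be answered.** The documents do not support this. Week 24 values can be compared between randomised arms without any baseline.
- **That the DLco effect would be diluted because Day 29 would serve as baseline.** With linear onset, 4/24 = 17% of the Week 24 effect would be subtracted. No section proposes Day 29 as a baseline, and linear onset is an assumption. Protocol 2.2 expects lung function to improve only some time after inflammation has subsided, which would make the share smaller. The figure is hypothetical and is not part of this finding.

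**Conclusion.** The point holds as an inconsistency. The schedule as read shows no pre-dose DLco, while the secondary objective and SAP 6.2.1 require one and the text implies one. If sites follow the table, DLco change from baseline is lost irrecoverably for their patients, and only an unadjusted Week 24 comparison remains.

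The severity is minor to moderate. DLco is one of about a dozen parameters in one secondary objective and is analysed descriptively in a non-confirmatory study. The primary analysis is untouched. The conclusion assumes that the machine-read row matches the original PDF. If the marks in the PDF run from Day 1 to Day 169, the missing-baseline finding falls away, and only the absence of an explicit DLco baseline definition in the SAP remains.

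**What to change.** 1. Check the DLco row of the Protocol 8.1 schedule against the original PDF.
2. If Day 1 is empty there, mark DLco on Day 1. Footnote 12 already makes that test pre-dose.
3. Reconcile the schedule with the description of full pulmonary function tests in Protocol 2.2 and with the baseline statements in Protocol 3.1 and 4, so that the text says which tests are taken on Day 1.
4. State in SAP 6.2.1 that the Day 1 value is the DLco baseline.

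The cost is one cell in the schedule, one sentence in the SAP and a slightly longer Day 1 visit. Adding the test raises the count from seven to eight. Moving the Day 29 test to Day 1 keeps it at seven but gives up the Week 4 point in the over-time graphs of Protocol 11.5.1.3. Because the exploratory objectives are redacted, the sponsor must first confirm that none of them needs the Day 29 value.
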